5.3 Biopsy and implant procedure

In the operating room, patient will be anesthetized per clinical routine for brachytherapy, and placed in dorsal lithotomy position. A transrectal ultrasound (TRUS) probe will be placed into the rectum for prostate visualization. The perineum will be prepped in sterile fashion.

TRUS images will be captured and fused with the MRI to identify the regions of prostate cancer involvement to be targeted. Transperineal biopsy will be carried out under TRUS guidance, with ≥ 4 cores targeted per MRI-defined region of involvement / clinically palpable region. The number of biopsy cores taken is not to exceed 12 (twelve) cores.

Following completion of the biopsy portion of the procedure, patient will undergo brachytherapy per usual clinical routine.

Biopsy samples will be processed for paraffin embedding and pathologic confirmation of tumor tissue presence (handled and stored by [name] laboratory). Analyses for DSBs will be performed using assays for TUNEL, 53bp1, and gamma h2ax. Approximately 1/3 of tissue will be frozen and set aside for future potential laser dissection capture for RNA sequencing (handled and stored in [name] laboratory).

Staff from [name] laboratory will arrange collection and archiving of diagnostic material. This will consist of the slides and/or paraffin blocks from the biopsies (both pretreatment and postflutamide/pre-brachytherapy).

Central pathology review will be performed for patients who have agreed / opted to allow us access to any post-treatment biopsies, if performed in routine clinical care, and retrospective review of baseline diagnostic pathologies. Formalin fixed biopsy tissue may be used for correlative DNA methylation analysis.

5.4 Follow-up evaluation

Patients will be assessed per routine clinical practice at 1-month and 6 months post-implant, at which time serum and urine specimens will be collected for exploratory analyses. They will receive considered off trial following the 6-9 month follow-up visit.

6.0 Data Analysis and Statistical Considerations

6.1 Study Design and Endpoints

This pilot study is to preliminarily evaluate if DNA double strand breaks occur in prostate cancer tissue following pulse-dose Flutamide administration in patients who are androgen suppressed. It consists of two parts, a run-in part and randomization part. The run-in part is to preliminarily determine feasibility, i.e., if DNA double strand breaks can be observed, defined as if there are greater than or equal to 5% of prostate cancer cells having gammaH2AX foci. The randomization part aims to better characterize the estimation precision of proportion of prostate cancer cells having gammaH2AX foci with and without Flutamide. During the randomization part, we will continue to monitor the feasibility of observing DNA double strand breaks (see Section 6.3 for details).

6.2 Sample Size Justification and Accrual

This is a pilot trial, and will be utilized to design a larger study to establish measures for such parameters with a reasonable level of precision. We will enroll 30 patients onto the trial, with goal of at least 24 evaluable patients accrued.

In the run-in phase, a total of 6 evaluable patients will be accrued to receive Flutamide administration. We will use a Bayesian monitoring rule to determine if the study is feasible. Specifically, we would consider it is “infeasible” if the probability of not observing greater than or equal to 5% of prostate cancer cells having gammaH2AX foci is more than 50%. Based on the Bayesian monitoring rule in Section 6.3, if there is less than or equal to 1 out of 6 cases with detectable DNA double strand breaks (i.e., greater than or equal to 5% of prostate cancer cells having gammaH2AX foci on patient level), the study will be considered as infeasible and will not proceed into the randomization part.

If the study proceeds into the randomization part, a total of 18 evaluable patients will be randomized in a 2:1 ratio to either receive Flutamide (12 patients) or not (6 patients). A total of 18 patients treated with Flutamide (6 from run-in and 12 from randomization) will produce a two-sided 90% confidence interval with a width ranging from 0.35 to 0.42 (if the true proportion of prostate cancer cells having gammaH2AX foci is 30%-80%). A total of 6 patients in control will produce a two-sided 90% confidence interval with a width approximately less than 0.5 (if the true proportion of prostate cancer cells having gammaH2AX foci is less than 10%).

All eligible patients will be offered enrollment on the study, and we estimate a 20% dropout and nonevaluable rate. Patients who drop out prior to the biopsy/brachytherapy procedure will be replaced; patients who drop out after biopsy/brachytherapy will not be replaced. In order to ensure at least 24 evaluable patients are available, we plan to enroll ~30 patients onto this trial. Given the minimal addition to standard therapy and effort requirement from patient, we expect to accrue at least 2-3 patients/month, and the full accrual will be completed in 2 years.

6.3 Early Stopping for Feasibility

The feasibility of detecting DNA double strand breaks will be based on the proportion of patients not observing greater than or equal to 5% of prostate cancer cells having gammaH2AX foci. We consider it is “infeasible” if the probability of not observing detectable DNA double strand breaks (detectable if greater than or equal to 5% of prostate cancer cells having gammaH2AX foci) is more than 50% and with more than 70% posterior probability. We assume there will only be a smaller proportion of cases in which DNA double strand breaks cannot be observed, e.g., on average only 10% of patients will not have detectable DNA double strand breaks and there will be about 16% chance that the risk will be 20% or more. This corresponds to a Beta(0.1,0.9) prior distribution. Table 6.3.1 summarizes the continuous stopping rule for the 18 evaluable patients treated with Flutamide. The feasibility stopping rule calls for the study to be stopped and will not proceed into the randomization part if there are less than or equal to 1 patients with detectable DNA double strand within the first 6 patients (in the run-in part). If the trial enters randomization part, the feasibility stopping rule calls for accrual suspension if the number of patients with detectable DNA double strand breaks is too low (equivalently, the number of patients without detectable DNA double strand breaks is too high).

Table 6.3.1 Stopping rule for feasibility

# patients without detectable DNA double strand breaks	5	6	7	8	9	10	11
Out of total # evaluable patients	6-7	8-9	11	12-13	14-15	16-17	18

Table 6.3.2 summarizes the operating characteristics based on 5,000 simulations with 18 evaluable patients in terms of how frequent the study would stop based on the stopping rule under different hypothetical feasibility rates, as well as the average sample sizes.

Table 6.3.2 Operating characteristics of the stopping rule for feasibility

Underlying proportion without detectable DNA double strand breaks	0.4	0.5	0.6	0.7	0.8
% of time study stops	19.3%	44%	74.8%	92.4%	99.4%
Expected sample size	16.3	14.1	11.1	8.7	6.9

6.4 Gender and Minority Compliance

Minorities of all races and ethnic groups are eligible for this study and will be encouraged to participate. In conformance with the National Institute of Health Revitalization Act of 1993 with regard to inclusion of women and minority in clinical research, we have also considered the possible interaction between race and treatments. Based on the current demographic trends in our center, we project that 24% of men in this study will be nonwhite. Women do not develop prostate cancer and therefore will not be enrolled.

7.0 Risks/Benefits Assessment

Patients enrolled onto this trial would undergo brachytherapy under anesthesia whether or not they participate in this trial. Therefore, the risks that are associated with the brachytherapy are not risks associated with the research. Similarly, we will only enroll patients who are undergoing androgen suppression as standard of care based on disease characteristics. Furthermore, patients would undergo the standard pre-treatment and post-treatment assessments/studies that are outlined in section 4.7 whether or not they participate in this trial.

Transperineal biopsy under anesthesia – Patient will undergo partial-gland transperineal biopsies as a result of enrollment on this trial. The risks of these biopsies is similar to that of standard prostate biopsies but with less chance of infection or sepsis due to not accessing through the rectum, as well as only targeting regions of known involvement. For comparative purposes, patients who undergo active surveillance have yearly biopsies performed for up to several years in succession until progression, therefore 1 partial-gland biopsy associated with this protocol is relatively modest.

Risk of Flutamide – Flutamide is an FDA approved drug with indication for use in patients with prostate cancer. Since we are only giving a single 250mg dose of Flutamide (compared to standard daily 250mg TID dosing for 4 months or more), it is a very low likelihood that patients will experience any long-lasting toxicity. It is theoretically possible that patients could have an acute adverse reaction, although this is expected to be rare.

Risk of blood draw

Patients will undergo blood sampling prior to the biopsy for pharmacokinetic analysis; patients who opt to participate in the exploratory endpoints will have additional blood draws. There could be pain or unexpected excessive bleeding and/or swelling related to the blood draw(s).

7.1 Psychological Risks - There are no foreseeable psychological risks associated with this protocol.

7.2 Social Risks – There are no foreseeable social risks associated with this protocol

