Moreover, RNAi-mediated knockdown of either AR- or topoisomerase 2 beta (TOP2B) prevented DSBs resulting from FLU exposure, which is consistent with mechanistic observations following stimulation with DHT⁶. Importantly, although LNCaP cells have a mutation in the AR increasing its activity, we also observed DSB formation in VCaP, CWR22Rv1, and LAPC4 cells as well, suggesting that PCa cells with wild-type AR will respond similarly. γH2AX foci increased over 6h exposure to DHT or FLU, yet this increase in γH2AX could be prevented by co-incubation with the antioxidant *N*-acetyl-*L*-cysteine (NAC, 5mM), suggesting that reactive oxygen species (ROS) contribute to the TOP2B-mediated DNA damage following AR signaling. To test the possibility that AR-mediated DSBs may radiosensitize AR-expressing PCa cells, DHT and AR-antagonists were used to induce DSBs in androgen-deprived LNCaP cells, followed by exposure to IR. Interestingly, a pulse of DHT or FLU significantly and synergistically enhanced the radiosensitivity of AR-positive VCaP prostate cancer cells (Fig 2A). Stimulation of castrated nude mice implanted with prostate cancer xenografts with a pulse of FLU followed by treatment with ionizing radiation also led to significant growth inhibition of the xenografts compared to mice treated with FLU alone or ionizing radiation alone, suggesting therapeutic benefit of the paradigm *in vivo* (Fig 2B).

Fig. 2. (A) Profound synergy of FLU plus IR in reducing clonogenic survival of VCaP cells *in vitro*. (B) Combination of a pulse of FLU followed by 6 Gy IR inhibits VCaP xenograft growth significantly greater than either agent alone.

Importantly, in these *in vivo* studies, immunohistochemical examination of biopsies from xenograft tissue displayed increased γH2AX foci, which increased from 0-12 hours and returned to basal levels by 24 hours. Similarly, AR was observed to be highly nuclear in localization under similar time-points (Fig 3).

These observations, if confirmed in humans, are potentially readily translatable to clinical practice. Such an effect would enhance the therapeutic index given its high specificity to AR-expressing tissues, and could be exploited on a repeated basis over a course of fractionated RT by dosing FLU at spaced intervals.

Fig. 3. AR in VCaP xenograft tissue biopsies following OH-Flu exposure in castrated setting

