5.1 Pre-implant Flutamide vs placebo dosing

Patients will receive either Flutamide single 250mg dose or placebo, taken orally 6-12 hours prior to the brachytherapy.

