7.3 Legal Risks – There are no legal risks associated with this protocol

7.4 Economic Risks – There are no economic risks associated with this protocol. Any costs that are not part of the patient's standard of care for brachytherapy and standard follow-up will be paid for by research funds.

7.5 Privacy/Confidentiality Risks – All research personnel involved in this trial will comply with HIPAA regulations. Because the data that is collected will contain personally identifiable information the following measures will be taken to minimize the risk of breaching patient confidentiality:

- Patients' clinical data (hard and soft copies) will be stored in locked confidential files in the Radiation oncology protocol office at Johns Hopkins east Baltimore campus, and on encrypted, restricted-access servers within the Radiation Oncology domain.
- Only the study personnel, the Johns Hopkins Clinical Research Office, the Office of Human Research Protection (OHRP), the Johns Hopkins Institutional Review Board, and other regulatory agencies will have access to the study files. The secured Clinical data includes: case report forms, source documentation, signed consent forms, and any material containing patient identifying information.
- This data will be securely stored in the Radiation Oncology protocol office at Johns Hopkins as long as required by governmental regulations.
- All of the agencies noted above who have access to study documents and patient identifier codes are to keep the identity of all subjects on this trial confidential. No information by which patients can be identified will be published.

7.6 Benefits – There is no expectation that patients will benefit from their participation in this study. There is the potential benefit that through participation subjects in the Flutamide arm will receive treatment that is more effective against their prostate cancer.

7.7 Payments and Compensation – Patients will not be paid or compensated for their participation in this trial.

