8.2 Definitions

Serious Adverse Event: means an event that is

- fatal
- life-threatening
- persistent or significantly disabling or incapacitating
- inpatient hospitalization or prolongation of hospitalization
- congenital anomaly or defect and/or
- a significant medical incident (considered to be a serious study related event because, based upon appropriate medical judgment, it may jeopardize the subject and may require medical or surgical intervention to prevent one of the outcomes listed in this definition.)

Important Adverse Event: means an event, although not a Serious Adverse Event, which still presents an undesirable occurrence that interferes with the subject's usual activities and may be persistent or require treatment. (For example, serious rash, cough, or fever.)

Unanticipated Adverse Event: means an event that results from a study intervention and was not expected or anticipated from prior experience. This includes expected events that occur with greater frequency or severity than predicted from prior experience.

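### Section 7.0 rules out brachytherapy toxicity as a research risk although the study drug is a candidate radiosensitiser, and non-serious post-implant toxicity has no planned collection by arm

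*Combined protocol and SAP*

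**What the plan says.** Section 7.0 starts from the point that "Patients enrolled onto this trial would undergo brachytherapy under anesthesia whether or not they participate in this trial" and concludes: "Therefore, the risks that are associated with the brachytherapy are not risks associated with the research". Its flutamide paragraph covers toxicity of the drug itself and acute reactions. Neither it nor any other risk paragraph mentions an interaction with radiation.

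The Background (Section 1.0) gives the rationale. In vitro: "Interestingly, a pulse of DHT or FLU significantly and synergistically enhanced the radiosensitivity of AR-positive VCaP prostate cancer cells". In xenografts, flutamide followed by radiation inhibited growth more than either alone. On selectivity: "Such an effect would enhance the therapeutic index given its high specificity to AR-expressing tissues". The γH2AX foci in xenograft tissue are described as ones "which increased from 0-12 hours and returned to basal levels by 24 hours".

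Under Section 5.1 the dose is "taken orally 6-12 hours prior to the brachytherapy", and under Section 5.3 the implant follows the biopsy in the same session. Section 7.6 first says no benefit is expected, then allows that "subjects in the Flutamide arm will receive treatment that is more effective against their prostate cancer".

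Section 8.0 says no adverse events are expected, describes the trial as one of a treatment planning system, and refers to Section 4.7 for follow-up. It commits the team to reporting serious or unexpected events and adopts CTCAE 4.0. Section 8.2 defines an unanticipated event as one resulting from a study intervention and adds: "This includes expected events that occur with greater frequency or severity than predicted from prior experience".

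**The concern.** The argument in 7.0 is sound for brachytherapy alone. Outside the trial, however, these patients would not take the pre-implant study dose. If that dose changes the tissue response to radiation, the change is a consequence of the research even though the implant is not. The protocol entertains such a change as a possible benefit in 7.6 but nowhere lists the corresponding possible harm.

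Two things are at stake. The risk statement is incomplete on the protocol's own premises. And Section 6.2 says this pilot will be used to design a larger study. That study would inherit an assertion that brachytherapy toxicity is not a research matter, without graded by-arm data to support or question it.

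**Working it through.** The plan states no figure on this point, so there is none to reproduce. The check compares sections and adds two small calculations.

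**1. Timing.** Dose-to-implant interval: 6-12 h (Section 5.1; the calendar in 4.5 agrees). Foci in xenografts: rising over 0-12 h, basal by 24 h (Background). The whole dosing interval lies inside the period of rising foci.

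**2. Is active drug still present at implant?** Inputs from Section 9.0: time to peak of the active metabolite about 2 h (normal adults) or 2.7 h (geriatric, single dose); half-life about 6 h or 8.1 h respectively; geriatric single-dose peak 894 ng/mL. Assuming mono-exponential decline after the peak, the share of peak remaining at time t is 0.5^((t − Tmax)/half-life).

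| Inputs | 6 h | 12 h |
|---|---|---|
| Tmax 2 h, half-life 6 h | 0.5^(4/6) = 63% | 0.5^(10/6) = 31% |
| Tmax 2.7 h, half-life 8.1 h | 0.5^(3.3/8.1) = 75% | 0.5^(9.3/8.1) = 45% |

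So roughly 63-75% of peak remains at 6 h and 31-45% at 12 h.

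**3. Can the size of an effect be derived?** No. The Background equates breaks at 10 µM in vitro with 0.5-2 Gy. With the geriatric values, plasma levels are about 894 × 0.754 = 674 ng/mL at 6 h and 894 × 0.451 = 403 ng/mL at 12 h. Taking hydroxyflutamide as flutamide plus one oxygen (276.22 + 16 ≈ 292 g/mol), these are about 2.3 and 1.4 µM, some 4 to 7 times below 10 µM. Section 9.0 also reports 92-94% protein binding at steady state. The documents give no normal-tissue data, isotope or dose rate. The Gy equivalence should not be carried over to patients.

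**4. What would capture a change in toxicity?**
- *Fatal events:* reported whatever the view on relatedness (8.1).
- *Serious or unexpected events:* reported (8.0, 8.1).
- *Expected events in excess:* covered by 8.2 if judged to result from a study intervention. Cause is established case by case under 8.3.
- *DSMB:* reviews toxicity at least annually (Section 16).
- *Non-serious events of an expected brachytherapy type:* no planned collection. The calendar has no toxicity row; its post-implant entries are PSA/testosterone, plasma and urine. Section 5.4 describes routine assessment plus specimens. Section 4.6 ties data collection to the listed procedures, with abstraction from clinic notes but no toxicity item. Section 4.7, cited in 7.0 and 8.0, is not in the text; Section 4 ends at 4.6.

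**5. What could a by-arm table show?** Flutamide 6 + 12 = 18 patients; placebo 6. With 0 events in 18, the one-sided 95% upper bound is 1 − 0.05^(1/18) = 15.3%. Two-sided 5% Fisher power for 18 v 6, under assumed toxicity rates (none are in the documents):

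| Placebo v flutamide | Power |
|---|---|
| 10% v 30% | about 1% |
| 20% v 40% | about 4% |
| 10% v 50% | about 22% |

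Only description is feasible.

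**The case against.** The strongest reply is that 7.0 is a risk narrative, not an attribution rule. Attribution sits in 8.3, and the routes in step 4 remain open whatever 7.0 says. This stands. A reader might infer that excess brachytherapy toxicity could not surface at all; Sections 8 and 16 do not support that. What remains is the non-serious, expected-type event.

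A reader might also infer that the interval was chosen so that breaks coincide with the implant. No section gives the reason for 6-12 h, and the biopsy endpoint alone would explain it. Only the overlap is documented. Nor do the documents show that this is the trial's main harm, that the whole gland is implanted, or that rectal or sexual toxicity follows from the mechanism. The Background argues for selectivity and a better therapeutic index, and the rat data in Section 9.0 show preferential accumulation only in the prostate. But the selectivity claimed is for AR-expressing tissue, which is wider than cancer, and it is a preclinical argument.

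Finally, flutamide with radiation is not new: Section 9.0 describes 231 patients given flutamide three times daily with goserelin before and during radiation. That is fair context. However, the protocol reports no toxicity from that trial, and the regimen was not a single pulse after androgen suppression.

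None of these replies rescues the inference in 7.0. An interaction of unknown size is a reason to list it as possible.

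**Conclusion.** The point holds in limited form. The 7.0 statement conflicts with the Background, with the timing overlap and with the potential benefit in 7.6, and a possible change in radiation toxicity appears nowhere as a research risk. The practical gap is confined to non-serious toxicity of an expected brachytherapy type, which has no planned grading or by-arm summary. It concerns 18 of 24 evaluable patients (75%).

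The contradiction rests on the text alone. The drug-level figures assume mono-exponential decline and show only that active metabolite is likely still present at implant. They do not show that normal tissue is harmed, and the documents support no estimate of such harm. This should be corrected before the pilot is used to design a larger study; it is not evidence that the trial is unsafe.

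**What to change.** 1. **Section 7.0.** Reconcile it with the Background and 7.6: keep the statement that brachytherapy itself is standard care, and add that the study drug could alter its toxicity and that this is a possible research risk of unknown size.
2. **Section 8.0.** Replace the treatment-planning description with one of this trial, correct the reference to 4.7 (also in 7.0), and revisit the statement on expected events. Add that post-implant toxicity is not to be judged unrelated solely because brachytherapy is standard care; relatedness stays case by case under 8.3.
3. **Calendar (4.5) and data collection (4.6).** Add CTCAE 4.0 grading of post-implant toxicity at the existing 4-week and 6-month visits. Tabulate it descriptively for run-in flutamide (6), randomised flutamide (12) and placebo (6) for the DSMB, prepared so that the blind is kept. State that 18 v 6 cannot support a formal comparison.

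Cost: a protocol amendment, slightly more data entry at two existing visits, and more events recorded as possibly related. No additional patients or visits are needed, and dosing, timing and clinical management are unchanged.
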